5 STUDY DESIGN

Subjects age 18-49 years will be stratified by their prior vaccination history, followed by randomized assignment to receive one of three licensed vaccines: Fluzone SD, Fluzone HD and Flublok. Block randomization will be performed separately for the two groups. Study subjects who participated in a previous year can be re-enrolled and receive the same vaccine as previously (Fluzone SD, Fluzone HD, Flublok, Flucelvax). Because the goal of the protocol is to evaluate the immune response to the vaccine and is not intended as a formal comparison of the adverse event profile, the vaccine assignment is not blinded. Following vaccination, subjects will have blood sample obtained at the time points illustrated above. The last study visit will take place 6 months after vaccination.

6 STUDY POPULATION

Up to 500 subjects will be enrolled from the existing population of healthy adults residing in Rochester, NY and within the University of Rochester community, males and non-pregnant females aged 18-49 years, inclusive. Pregnancy status will be verified at screening and enrollment prior to vaccination. Women of childbearing potential will be asked to use a barrier method of birth control or an FDA approved form of birth control.

Study subjects will be recruited via placement of flyers in key locations on campus. Based on previous experience, we anticipate enrollment of 40 to 60 percent non-pregnant females in the study.

6.1 Inclusion Criteria

Subjects must meet all of the following inclusion criteria to participate in this study:

1. Aged between 18 and 49 years of age (inclusive). (Participants who are returning for a subsequent year may be ≥ 50 years.)
2. Female subjects of childbearing potential must fulfill one of the following: (i) not able to bear children because she has been surgically sterilized (tubal ligation or hysterectomy) or (ii) agrees to practice effective methods of contraception that may include, but are not limited to abstinence, barrier methods, monogamous relationship with vasectomized partner, birth control pills, patches, hormonal shots or hormonal implants, NuvaRing and IUDs (intrauterine devices), from 30 days prior to study enrollment through 30 days following receipt of the last dose of vaccine.
3. Female subjects of childbearing potential must have a negative urine pregnancy test within 24 hours prior to vaccination.
4. Are in good health¹.

¹As determined by medical history and targeted physical examination to evaluate acute or currently ongoing chronic medical diagnoses or conditions, defined as those that have been present for at least 90 days, which would affect the assessment of the safety of subjects or the immunogenicity of study vaccinations. Chronic medical diagnoses or conditions should be stable for the last 60 days. This includes no change in chronic prescription medication, dose, or frequency as a result of deterioration of the chronic medical diagnosis or condition in the 60 days prior to enrollment. Any prescription change that is due to change of health care provider, insurance company, etc., or that is done for financial reasons, as long as in the same class of medication, will not be considered a deviation of this inclusion criterion. Any change in prescription medication due to **improvement** of a disease outcome, as determined by the site principal investigator or appropriate sub-investigator, will not be considered a deviation of this inclusion criterion. Subjects may be on

chronic or as needed (prn) medications if, in the opinion of the site principal investigator or appropriate sub-investigator, they pose no additional risk to subject safety or assessment of reactogenicity and immunogenicity and do not indicate a worsening of medical diagnosis or condition. Similarly, medication changes subsequent to enrollment and study vaccination are acceptable provided there was no deterioration in the subject's chronic medical condition that necessitated a medication change, and there is no additional risk to the subject or interference with the evaluation of responses to study vaccination. Note: Topical, nasal, and inhaled medications (with the exception of inhaled corticosteroids as outlined in the Subject Exclusion Criteria (see Section 5.1.2), herbals, vitamins, and supplements are permitted.

5. Have normal vital signs (heart rate >55 to <100 bpm; blood pressure: systolic \geq 90 mm Hg and \leq 150 mm Hg; diastolic \leq 90 mm Hg; oral temperature <100.0°F);
6. The subject is able to understand and comply with the planned study procedures, including being available for all study visits.
7. The subject has provided informed consent prior to any study procedures.

6.2 Exclusion Criteria

Subjects who meet any of the following exclusion criteria at baseline cannot participate in the study:

1. Subject report of known hypersensitivity to allergy to components of the study vaccine or other components of the study vaccine.
2. Subject report of a history of severe reactions following previous immunization with licensed or unlicensed influenza virus vaccines.
3. Subject report of a history of Guillain-Barre syndrome within 6 weeks of receipt of a previous influenza vaccine.
4. The subject is a woman who is pregnant or breastfeeding or intends to become pregnant during the study period between enrollment and 30 days following receipt of vaccine.
5. The subject is immunosuppressed as a result of an underlying illness or treatment with immunosuppressive or cytotoxic drugs, or use of anticancer chemotherapy or radiation therapy within the preceding 36 months.
6. The subject received immunoglobulin or another blood product within the 3 months prior to enrollment in this study.
7. The subject has an active neoplastic disease (excluding non-melanoma skin cancer or prostate cancer that is stable in the absence of therapy) or a history of any hematological malignancy. For this criterion, "active" is defined as having received treatment within the past 5 years.
8. The subject has long-term (greater than 2 weeks) use of oral or parenteral steroids

9. The subject has received an inactivated vaccine within the 2 weeks or a live vaccine within the 4 weeks prior to enrollment in this study or plans to receive another vaccine within the next 28 days.
10. The subject has an acute or chronic medical condition that, in the opinion of the investigator or appropriate sub-investigator, would render vaccination unsafe or would interfere with the evaluation of responses. These conditions include any acute or chronic medical disease or conditions defined as persisting for 3 months (defines as 90 days) or longer, that would place the subject at an unacceptable risk of injury, render the subject unable to meet the requirements of the protocol, or may interfere with the evaluation of responses of the subject's successful completion of the study.
11. Subjects with an active infection or that has an acute illness or an oral temperature greater than 99.9F (37.7C) within 3 days prior to enrollment or vaccination. Subjects who had an acute illness that was treated symptoms resolved are eligible to enroll as long as treatment is completed and symptoms resolved > 3 days prior to enrollment.
12. The subject is currently participating or plans to participate in a study that involves an experimental agent (vaccine, drug, biologic, device, blood product, or medication) or has received an experimental agent within 1 month prior to enrollment in this study, or expects to receive another experimental agent during participation in this study, or intends to donate blood during the study period.
13. The subject has any condition that would, in the opinion of the site investigator, place the subject at an unacceptable risk of injury or render the subject unable to meet the requirements of the protocol.
14. Have been hospitalized for psychiatric illness, history of suicide attempt, or confinement for danger to self or others, within the past 10 years.
15. The subject has a diagnosis of schizophrenia, bi-polar disease, or other severe (disabling) chronic psychiatric diagnosis, or is receiving psychiatric drugs. Subjects who are receiving antidepressant drugs and are stable for at least 3 months prior to enrollment without decompensation are allowed enrollment into the study.
16. The subject has a history of alcohol or drug abuse in the 5 years prior to enrollment.
17. The subject has a known human immunodeficiency virus, hepatitis B, or hepatitis C infection.
18. The subject has any condition that the principal investigator (PI) believes may interfere with successful completion of the study.

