Because it is possible that prior exposure will impact the relative impact of peptide specific help on the antibody response, subjects will be screened for pre-vaccination antibody. Subjects will be divided into relatively high (greater than 1:8) or low (equal to or less than 1:8) pre-vaccination antibody based on pH1N1. The basic study design for the healthy adults age 18-49 years is described below. Subjects will be queried regarding prior history of influenza vaccination, and stratified into those who have not been vaccinated in the previous year and those who have, followed by randomized assignment to receive one of four licensed vaccines. Study subjects who participated in a previous year can be re-enrolled and will receive the same vaccine they received previously. Because the goal of the protocol is to evaluate the immune response to the vaccine and is not intended as a formal comparison of the adverse event profile, the vaccine assignment is not blinded. Following vaccination, subjects will have samples of blood obtained at the time points illustrated above. The last study visit will take place approximately 6 months after vaccination in order to test the durability of the response.

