4.2 Outcome Measures

4.2.1 Primary Outcome Measures

The primary outcome measure for this study is:

- Mean change in the specificity, quantity and quality of serum antibody titers to the vaccine viruses, pH1N1, H3 and influenza B using HAI (year 1-5) and MN for pH1N1 and H3 viruses (years 1-5 from Day 0 to Day 28)

- Mean change in the CD4 T cell reactivity to pools of total pHA peptides derived from the pH1N1 HA, as well as H3, influenza B HA, NP, and M1 peptides will be quantified using cytokine Elispot From Day 0 to Day 14

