8.2 Vaccination (Defined as Day 0)

Subjects will be considered enrolled if they have signed the consent form. However, only subjects who met the entry criteria will be vaccinated and followed. Note that the screening visit and the vaccination visit may take place on the same day. At the vaccination visit the following procedures will be performed.

- An interim medical history will be obtained (unless the screening and vaccination visit are the same) including concomitant medications, detailing any subsequent medical events the subject has experienced since the screening visit.
- A directed physical exam will be performed, if indicated by the interval history, directed at the relevant portions of the exam.
- A urine pregnancy test will be obtained in female subjects. This test must be negative for the subject to continue in the study.
- The entry criteria will be reviewed with the subject and it will be verified that the subject continues to meet the entry criteria.

- A serum sample will be obtained from an arm vein for baseline antibody titers
- A sample of Peripheral Blood Mononuclear Cells (PBMC) will be obtained for assessment of baseline influenza-specific B cells and CD4 cells
- Subjects that were not vaccinated with influenza vaccine with the prior year's vaccine, will be randomized at the pharmacy into one of the three (FluBlok, Fluzone SD, Fluzone HD) vaccine groups, and will receive the indicated vaccine by intramuscular injection in open label fashion.
- Repeat subjects will receive the same vaccine they received previously. (FluBlok, Fluzone SD, Fluzone HD, Flucelvax)
- Subjects will be observed in the clinic for 30 minutes post vaccination for development of acute adverse events

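### No entry criterion excludes prior receipt of the current season's influenza vaccine, so a subject can be randomised with a Day 0 sample that may already be boosted

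*Combined protocol and SAP*

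**What the plan says.** **Eligibility.** Section 6.2, exclusion 9, applies if "The subject has received an inactivated vaccine within the 2 weeks or a live vaccine within the 4 weeks prior to enrollment in this study". It also applies if the volunteer "plans to receive another vaccine within the next 28 days". The look-back runs from enrolment, and Section 8.2 states: "Subjects will be considered enrolled if they have signed the consent form". Section 8.1 allows screening from Day -21 to Day 0, so consent can precede the Day 0 sample by up to 21 days.

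**Vaccine history.** Section 8.1 has it taken before group assignment. Its stated use is stratification, described in three ways:
- Section 1: subjects are "stratified into those who have not been vaccinated in the previous year and those who have".
- Section 5: "Subjects age 18-49 years will be stratified by their prior vaccination history".
- Section 8.2, randomisation step: "Subjects that were not vaccinated with influenza vaccine with the prior year's vaccine".

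**Outcomes.** Section 4.2.1 gives the antibody outcome as "Mean change in the specificity, quantity and quality of serum antibody titers to the vaccine viruses", measured from Day 0 to Day 28. The CD4 T cell outcome is a mean change from Day 0 to Day 14.

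**The concern.** The trial measures how a person responds to the assigned product, starting from a sample taken just before vaccination. Suppose a volunteer received this season's vaccine in the community a few weeks earlier. The Day 0 sample then may not be a pre-vaccination sample, and the change from Day 0 describes a second dose of the same season's antigens, possibly from a different product.

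Two features of the protocol make this matter. Section 3.1 says that antibody responses are smaller in people who start with higher titres. Section 3.3 builds the hypothesis on composition: HA alone against vaccines that also carry internal virion proteins. A Flublok recipient who recently had an egg-derived or cell-derived product is a poor test of that contrast.

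The protocol already treats a nearby vaccine as a problem in the forward direction. Exclusion 9 bars planned vaccines for 28 days, and Section 9.1 asks that licensed vaccines wait until 21 days after the study dose. A same-season dose before baseline is at least as relevant to these outcomes.

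**Working it through.** The documents give no figure on this point to reproduce. The check is a reading of the text, followed by an illustration of size.

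**1. Does any other criterion close the gap?** In Section 6.2, exclusions 2 and 3 concern severe reactions and Guillain-Barré syndrome after earlier influenza vaccines. Exclusion 12 concerns experimental agents. Exclusions 10, 13 and 18 are left to investigator judgement about conditions and do not name vaccination. The inclusion criteria in Section 6.1 do not mention a recent influenza vaccine. Some front matter and the design schematic were not available to check.

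**2. First permitted day.**
- Inactivated vaccine: 2 weeks = 14 days, so day 15 before enrolment passes.
- Live vaccine: 4 weeks = 28 days, so day 29 passes.

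**3. Interval to the Day 0 sample.** For the shortest inactivated interval that passes:
- consent on Day 0: 15 days
- consent on Day -21: 15 + 21 = 36 days

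The protocol's own response visits are Day 14 ± 1 (CD4) and Day 28 ± 2 (antibody). At 15 days the sample is already at the CD4 time point. At 36 days it is past both.

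**4. A dose between consent and Day 0.** This is not before enrolment. Unless it was already planned at consent, exclusion 9 does not reach it. Section 8.2 reviews the entry criteria again at Day 0, but the criterion under review is still anchored to enrolment.

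**5. Which stratum?** It depends on the meaning of the previous year.
- *Last season:* a subject vaccinated this season but not last falls in the unvaccinated stratum.
- *Last 12 months, or any prior history (Section 5):* the subject is pooled with people vaccinated about a year earlier.

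Neither reading removes the subject.

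**6. Illustration of size.** All inputs here are assumptions except the 45 per group and nominal 80% power in Section 12.2. Let p be the share of such subjects in each arm.

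*Fold rise.* Assume a 4-fold HAI rise in others (2 on the log2 scale). With no further rise in the affected subjects, the geometric mean is 2^(2(1 − p)). With half the log2 rise, it is 2^(2 − p).

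| p | No further rise | Half the log2 rise |
|---|---|---|
| 5% | 2^1.90 = 3.73 | 2^1.95 = 3.86 |
| 10% | 2^1.80 = 3.48 | 2^1.90 = 3.73 |
| 20% | 2^1.60 = 3.03 | 2^1.80 = 3.48 |

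*Power.* Assume affected subjects contribute no between-arm difference and the SD is unchanged. Using the normal approximation, power = Φ((1 − p)(1.960 + 0.842) − 1.960):
- p = 5%: Φ(0.70) = 76%
- p = 10%: Φ(0.56) = 71%
- p = 20%: Φ(0.28) = 61%

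If affected subjects contributed half the between-arm difference, replace p by p/2. Then 10% of subjects gives 76% and 20% gives 71%.

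**The case against.** The strongest reply is that this is a small drafting omission with partial safeguards.

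- **History is taken.** Section 8.1 collects vaccine history before assignment, so staff would probably notice such a volunteer. Section 10.1 describes vaccination as standard of care under the manufacturers' instructions, which does not suggest deliberate second doses in one season. Both are true, but neither is a written exclusion.
- **The analysis looks at baseline.** Section 12.4 compares vaccines within pH1N1 serostatus groups, relates baseline to boost, and plans mixed models with control for baseline. This limits the effect. It does not remove the subjects or distinguish a boost a few weeks old from a long-standing titre.
- **The sponsor accepted higher baselines.** Section 3.2 records that low-titre screening was dropped. That concerns long-standing immunity; it does not address a same-season dose weeks earlier.
- **The size is conjecture.** This stands. No frequency is given, and zero further rise is a worst case: Section 3.1 says responses are lower at high baseline, not absent.

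A reader might go further and infer that chance imbalance distorts the vaccine comparison. With 45 per group, an imbalance of two subjects shifts the difference by at most 2 × 2/45 = 0.089 log2 units in the worst case above. If the SD of the log2 rise is 1 to 2 (assumption), the standard error is SD × √(2/45) = 0.21 to 0.42, so the shift is about 0.2 to 0.4 standard errors. That variation is already in the standard error. The uneven prior vaccination in Section 3.2 (18/22, 16/22 and 13/26) shows that such imbalance occurs; it does not show bias.

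**Conclusion.** The concern holds as a gap in eligibility. The written rule admits subjects whose Day 0 sample, the baseline for both primary outcomes, may already reflect this season's vaccine. It should be corrected, but it does not invalidate the comparison.

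For newly randomised subjects the expected consequence is diluted and noisier change from Day 0, and a less clean composition contrast. The size is unknown and may be near zero. The illustrated power figures depend on the assumed share of subjects, their assumed lack of between-arm difference and an unchanged SD.

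Three stronger readings are not supported:
- *Systematic bias between arms.* Randomisation spreads these subjects on average.
- *An unvaccinated stratum shown to be contaminated.* That follows only if the previous year means last season; the documents leave the term open.
- *A 15-day threshold for every vaccine.* It applies to inactivated products; for live vaccine the first permitted day is 29.

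**What to change.** 1. Add to exclusion 9 receipt, at any time before vaccination on Day 0, of an influenza vaccine formulated for the current season.
2. Ask about it at screening and again at Day 0, because the present look-back stops at consent. Record the date and product.
3. State whether the previous year in the stratification rule means last season or the last 12 months, and use one wording in Sections 1, 5 and 8.2.
4. For subjects already enrolled, repeat the primary Day 0 to 14 and Day 0 to 28 comparisons without those who have a recorded current-season dose before Day 0. Use only history recorded before assignment, so that the omission rests on a pre-randomisation fact. Treat this as a sensitivity analysis and do not change the primary set: Section 8.1 does not say that the vaccination date is captured, so identification may be incomplete.

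The cost is one line in Section 6.2, one question asked twice, and one additional analysis. A few volunteers become ineligible each season.

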6.3 Handling of Withdrawals

Participants who withdraw, or are withdrawn or terminated from the study, or are lost to follow-up after receiving the assigned vaccine will not be replaced. Participants who consented to the

study but did not receive the influenza vaccine will be replaced. These subjects will be considered as screen failures.

6.4 Termination of Study

Although the study sponsor has every intention of completing the study, the sponsor reserves the right to terminate the study at any time for clinical or administrative reasons. Reasons for termination include, but are not limited to, study closure due to internal safety review and recommendation, or at the discretion of DMID.

7 STUDY INTERVENTION/INVESTIGATIONAL PRODUCT

7.1 Study Product Description

Fluzone Standard Dose (Sanofi Pasteur). Quadrivalent subvirion vaccine (IIV4) produced in embryonated hen's eggs and administered intramuscularly at a dose of 15 ug of HA (as determined by SRID) per component.

Fluzone High Dose (Sanofi Pasteur). Trivalent subvirion vaccine (IIV3) produced in embryonated hen's eggs and administered intramuscularly at a dose of 60 ug of HA (as determined by SRID) per component.

FluCeIVax (Novartis). Quadrivalent subunit vaccine produced in MDCK mammalian cell culture (ccIV4) administered intramuscularly at a dose of 15 ug of HA (determined by SRID) per component

FluBlok (Protein Sciences) Quadrivalent purified recombinant hemagglutinin vaccine (rIV4) produced in insect cells and administered intramuscularly at a dose of 45 ug of HA (determined by SRID) per component.

All four products are indicated for the prevention of influenza in adults, although Fluzone HD is only indicated for prevention in adults ages 65 and older.

7.1.1 Acquisition

All four vaccines will be ordered from the hospital pharmacy which will acquire the vaccine through distributors.

7.1.2 Formulation, Packaging, and Labeling

Fluzone HD and SD (Sanofi Pasteur)

Fluzone (Influenza Vaccine) for intramuscular injection is an inactivated influenza vaccine, prepared from influenza viruses propagated in embryonated chicken eggs. The virus-containing allantoic fluid is harvested and inactivated with formaldehyde. Influenza virus is concentrated and purified in a linear sucrose density gradient solution using a continuous flow centrifuge. The virus is then chemically disrupted using a non-ionic surfactant, octylphenol ethoxylate (Triton® X-100), producing a "split virus". The split virus is further purified and then suspended in sodium 12 phosphate-buffered isotonic sodium chloride solution.

Fluzone is standardized according to United States Public Health Service requirements and is formulated to contain HA of each of the influenza strains recommended for the current influenza season. Vaccine is formulated in sodium phosphate-buffered isotonic sodium chloride solution containing formaldehyde, octylphenol ethoxylate and gelatin, in single dose prefilled syringes

Flucelvax (Seqiris)

FLUCELVAX (Influenza Vaccine), a vaccine for intramuscular injection, is a “subunit” influenza vaccine prepared from virus propagated in Madin Darby Canine Kidney (MDCK) cells, a continuous cell line. These cells were adapted to grow freely in suspension in culture medium. The virus is inactivated with β -propiolactone, disrupted by the detergent cetyltrimethylammonium bromide and purified through several process steps. Each of the 3 virus strains is produced and purified separately then pooled to formulate the trivalent vaccine.

FLUCELVAX is a sterile, slightly opalescent suspension in phosphate buffered saline. FLUCELVAX is standardized according to United States Public Health Service requirements for the upcoming influenza season and is formulated to contain a total of 45 micrograms (mcg) hemagglutinin (HA) per 0.5 mL dose in the recommended ratio of 15 mcg HA of each of the three influenza strains recommended for that season/. Each dose of FLUCELVAX may contain residual amounts of MDCK cell protein (≤ 8.4 mcg), protein other than HA (≤ 120 mcg), MDCK cell DNA (≤ 10 ng), polysorbate 80 (≤ 1125 mcg), cetyltrimethylammonium bromide (≤ 13.5 mcg), and β -propiolactone (<0.5 mcg), which are used in the manufacturing process.

FLUCELVAX will be supplied in single dose, pre-filled syringes. The vaccine contains no preservative or antibiotics, but the tip caps of the pre-filled syringes may contain natural rubber latex.

Flublok (Protein Sciences Corporation)

Flublok [15] is a sterile, clear, colorless solution of recombinant hemagglutinin (HA) proteins from three influenza viruses for intramuscular injection. It contains purified HA proteins produced in a continuous insect cell line (expresSF+®) that is derived from Sf9 cells of the fall armyworm, *Spodoptera frugiperda*, and grown in serum-free medium composed of chemically-defined lipids, vitamins, amino acids, and mineral salts. Each of the three HAs is expressed in this cell line using a baculovirus vector (*Autographa californica nuclear polyhedrosis virus*), extracted from the cells with Triton X-100 and further purified by column chromatography. The purified HAs are then blended and filled into single-dose vials.

Flublok is standardized according to United States Public Health Service (USPHS) requirements to contain 45 mcg of each HA of the strains recommended for that season.

A single 0.5 mL dose of Flublok contains sodium chloride (4.4 mg), monobasic sodium phosphate (0.195 mcg), dibasic sodium phosphate (1.3 mg), and polysorbate 20 (Tween®20) (27.5 mcg). Each 0.5 mL dose of Flublok may also contain residual amounts of baculovirus and

host cell proteins (≤ 28.5 mcg), baculovirus and cellular DNA (≤ 10 ng), and Triton X-100 (≤ 100 mcg).

Flublok contains no egg proteins, antibiotics, or preservatives. Flublok will be supplied in single dose vials, and the stoppers used for the single-dose vials are not made with natural rubber latex.

